1.3 Do you need funding from Assiut Medical School Grants Office?

Yes No

1.4 ID of grant

2019-09-05-001-R1 .Funder: Grant office - faculty of medicine -Assiut university].

Part 2: Research Details

2.1 Background (Research Question, Available Data from the literature, Current strategy for dealing with the problem, Rationale of the research that paves the way to the aim(s) of the work). **(200-250 words max.)**

Ovarian germ cell tumors (OGCTs) constitute 10% of ovarian tumors in Egypt [1] and mainly affect young females [2]. Teratomas are the most common type [3]. Most of teratomas are benign. However, it is liable for malignant transformation [4]. Others are malignant including dysgerminoma, immature teratoma, yolk sac tumor, etc. [5] and accounts 1–1.5% of cancers in young females [6]. The pathogenesis of OGCTs is not clearly understood. Some authors revealed that mature cystic teratoma is a form of human parthenogenesis [7], which makes important concerns about future of fertility and germ stem cell replacement therapy [8].

P16 is a member of cyclin-dependent kinase (CDK) inhibitors. It arrests the cell cycle in G1 phase, so it is known as a tumor suppressor protein [9]. CDK inhibitors now are evolving as novel target therapies under clinical trials such as Palbociclib, Abemaciclib and Ribociclib that offer a hope for different cancers, such as breast cancer [10] and non-small cell lung cancer [11]. One member which is recently approved by US FDA is palbociclib for use in postmenopausal women with breast cancer [12]. Thus, it is necessary to do further researches on its expression among different neoplasms.

P16 immunohistochemical(IHC) expression has been widely investigated in different cancers. Its IHC expression is either absent [13] or overexpressed [14]. Overexpression of p16 is documented in HPV related endocervical neoplasms and HSILs of the vulvovaginal region [14]. Absence of p16 expression is detected in multiple cancers such as Lung cancer, colorectal cancer and lymphoma [15].

P16 IHC expression in OGCTs is poorly investigated. One study suggests that absent p16 is involved in proliferation of malignant OGCTs via molecular assessment [16]. Another study suggested that decreased P16 is involved in malignant transformation of MCT to SCC [17]. However, Previous studies are still limited and recommended further studies to confirm its results.

As the role of altered P16 protein in OGCTs is not widely investigated, we hypothesized that abnormal P16 expression may be involved in its pathogenesis and germ stem cell proliferation. Abnormalities may be found either in neoplastic or stromal components. The role of stromal component of OGCTs as tumor microenvironment has no published studies yet. This will give more information about molecular pathways of germ stem cell proliferation to give a hope for CDK inhibitors as novel target therapies in the management of OGCTs and new advances in use of germ stem cell replacement therapy.

2.2 Aim(s) of the Research (100 words max):

In this study , we aim to :

- 1-Evaluate the immunohistochemical expression of p16 in both neoplastic and stromal components of benign and malignant OGCTs and scoring its immunoreactivity.
- 2-Compare the immunohistochemical expression of p16 between different histopathological types of OGCTs.
- 3-Correlate between P16 immunohistochemical expression with clinicopathological parameters (Age, Histopathological type, grading, and staging).

2.3 Research Area (Faculty Research Plan). Choose one and delete the rest.

7

1. Basic researches that may lead to possible/definite improvement in health services and solving the above problems.

2.4. Research Methods and techniques:

The study protocol was approved by the Institutional Review Board at Faculty of medicine, Assiut University in December, 2019 (IRB No.17100871) and Ethical approval for this study was obtained from the committee of medical ethics, Faculty of medicine, Assiut University.

Type of the study: Matched case-control study.

Study Setting: IHC lab of Pathology department, Faculty of medicine, Assiut University.

Tissue sampling: Sixty-two formalin-fixed, paraffin wax-embedded ovarian specimens were obtained from departments of surgical pathology in Assiut University Hospital (AUH) and South Egypt cancer institute (SECI) from January 2010 to January 2021. These specimens includes:

(Group A) 22 malignant ovarian germ cell tumors (MOGCTs),

(Group B) 20 apparent normal ovarian tissue as a control group and

(Group C) 20 mature cystic teratomas as equal benign comparison group. **Group A** constitutes 5 dysgerminomas, 8 immature teratomas (four of them Grade II and the other four are Grade III, FIGO grading system) and 9 yolk sac tumors. The patients ranged in age from 12 to 23 years (median age 16.5 years). The initial diagnosis of each MOGCTs was re-evaluated according to the WHO Classification of Ovarian Tumors.

Group B includes normally apparent ovaries that surgically resected with specimens of total abdominal hysterectomy and salpingo-oopherectomy for non-ovarian, non-malignant causes as multiple fibroid uterus and adenomyosis as a **control** group. The patients ranged in age from 42 to 64 years (median **50** years old).

All available Hematoxylin and eosin stained slides were examined by two independent pathologists by routine light microscopy and the most representative one or two tissue blocks were used for immunohistochemical staining. The clinical and pathological data includes age, grade, stage, recurrence of lesions were evaluated according to pathological reports.

- **Immunohistochemistry:** The tissue samples were formalin-fixed, paraffin embedded tissue blocks, and were stored at room temperature. Thin sections of 4 um thickness were cut from selected representative tissue blocks, and were taken on to coated slides, kept in an oven at 70-C for 25 minutes, deparaffinized by washing in two containers of xylene for 15 minutes for each and rehydrated through serial dilutions (100% , 90% , 80% , 70 %) of alcohol for 5 minutes in each dilution. Then, sections were treated by 3% Hydrogen peroxide for 10 minutes to prevent nonspecific background followed by PBS buffer wash 4 times adequately. For antigen retrieval, the slides were kept in citrate buffer (PH = 6) and autoclaved at 90-C for 15 minutes and left to cool to room temperature. The slides were washed with PBS buffer 4 times adequately and the tissue sections were incubated with primary antibody; **p16INK4a Recombinant Rabbit Monoclonal Antibody (RM267) (MA5-27905)** at a dilution of 1:500 overnight, followed by incubation with secondary antibody; **Polyvalent polymer-HRP** for 10 minutes for each step followed by adequate 4 times of PBS buffer wash. The tissues were then treated with Diaminobenzidine chromogen (**DAP-chromogen**) for brown color development for 10 minutes. Then, sections were treated by **Mayer hematoxylin** as the counter stain for 2 minutes.

For sections received from malignant cases, we add additional **Ki67 IHC** staining as tissue sections after deparffinization and blocking by 3% hydrogen peroxidase were incubated with primary antibody; **Ki67 antibody (DAKO)**, ready to use for 20 minutes, followed by incubation with secondary antibody; **Polyvalent polymer-HRP** for 20 minutes, followed treatment with Diaminobenzidine chromogen (**DAP-chromogen**) for brown color development for 5 minutes. Then, sections were treated by **Mayer hematoxylin** as the counter stain for 2 minutes. The slides were washed by tap water, dehydrated through serial dilutions of alcohol, washed by xylene for a short period, and mounted with DPX.

The normal apparent ovarian tissues were used as controls. Sections from cervical non keratinized Squamous cell carcinoma with block p16 expression, were used as positive controls; and the tissue slides without the primary antibody treatment served as the negative controls.

-Immunohistochemical evaluation: For P16 IHC staining, the percentage of P16 positive cells and the location of positive signals (nuclear or cytoplasmic) were visually estimated for neoplastic components of all lesions. German Semi-quantitative scoring system were used to evaluate P16 expression as every tumor will be given a score according to the intensity of the cytoplasmic and nucleic staining (no staining = 0, weak staining = 1, moderate staining = 2, strong staining = 3) And the extent of stained cells (0% = 0, 1–10% = 1, 11–50% = 2, 51–80% = 3, 81–100% = 4). The final immunoreactive score will be determined by multiplying the intensity scores with the extent of positivity scores of stained cells, with the minimum score of 0 and a maximum score of 12 (score 0, 1,2,3,4,6,8,9 and 12). For Ki67 IHC staining for malignant cases, the labelling index for Ki-67 antigen was calculated as the percentage of tumor cells with distinct nuclear staining in the most evenly and distinctly labelled tumor areas in each section. At least 1000 tumor cells were counted for each section.

2.5-Data management and analysis:

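### The study is labelled matched, but no matching variable is named and malignant cases (12–23 years) and normal-ovary controls (42–64 years) do not overlap in age; if p16 is compared between them, the difference cannot be separated from age

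*Combined protocol and SAP*

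**What the plan says.** Section 2.4 (Research Methods and techniques) gives the design as "Type of the study: Matched case-control study". It lists three groups: 22 malignant ovarian germ cell tumours (Group A), "20 apparent normal ovarian tissue as a control group" (Group B) and "20 mature cystic teratomas as equal benign comparison group" (Group C).

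The ages in the same section are:

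- Group A: "The patients ranged in age from 12 to 23 years (median age 16.5 years".
- Group B: "The patients ranged in age from 42 to 64 years", with a median of 50. These ovaries were removed with hysterectomy specimens for benign, non-ovarian conditions.
- Group C: no age range or median is given.

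Age was available to the investigators: "The clinical and pathological data includes age, grade, stage, recurrence of lesions were evaluated according to pathological reports".

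Section 2.5 (Data management and analysis) plans ANOVA or an independent-samples Kruskal-Wallis test with Bonferroni post-hoc comparisons, and Spearman correlation. It contains no paired, conditional or stratified analysis and no age covariate. Age enters the plan only through Aim 3 in section 2.2, as one of the parameters to be correlated with p16.

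**The concern.** A matched case-control label tells the reader that at least one confounder was controlled when the controls were selected. Here neither the sampling description nor the analysis supports that. No matching variable, ratio or procedure appears in the available text, and the tests are those for independent groups.

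Age is an obvious candidate for matching, and on age the two groups are completely separate. If p16 is compared between malignant tumours and normal ovary, every specimen in one arm comes from an adolescent or young adult and every specimen in the other from a woman in middle age or later. A difference could reflect neoplasia, age, or both, and these data could not tell them apart.

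Aim 3 faces the same problem in reverse. If Group B is pooled into the correlation of p16 with age, any difference between tumour and normal tissue will appear as an age correlation.

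**Working it through.** **Inputs (all from section 2.4).** Group A: n = 22, minimum 12, maximum 23, median 16.5. Group B: n = 20, minimum 42, maximum 64, median 50. Group C: n = 20, ages not stated.

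**Step 1: the plan's own counts.** 22 + 20 + 20 = 62, the stated total. The subtypes in Group A are 5 dysgerminomas + 8 immature teratomas + 9 yolk sac tumours = 22. Both agree.

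**Step 2: overlap.** Youngest control minus oldest case: 42 − 23 = 19 years. No A–B pair could be matched on age within any tolerance under 19 years. Difference in medians: 50 − 16.5 = 33.5 years.

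**Step 3: limits on the mean ages.** With an even n, the median is the average of the two middle values. The mean is smallest when the values below the middle sit at the minimum and those above it sit at the median (except the one maximum). It is largest in the mirror case.

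- A, smallest: (10 × 12 + 2 × 16.5 + 9 × 16.5 + 23) / 22 = 324.5 / 22 = 14.75
- A, largest: (12 + 9 × 16.5 + 2 × 16.5 + 10 × 23) / 22 = 423.5 / 22 = 19.25
- B, smallest: (9 × 42 + 2 × 50 + 8 × 50 + 64) / 20 = 942 / 20 = 47.1
- B, largest: (42 + 8 × 50 + 2 × 50 + 9 × 64) / 20 = 1118 / 20 = 55.9

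The difference in mean age therefore lies between 47.1 − 19.25 = 27.85 and 55.9 − 14.75 = 41.15 years, that is, 27.9 to 41.2. This needs no assumption about the shape of either age distribution.

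**Step 4: can the analysis repair it?** There is no age at which both groups have specimens. An age-adjusted A–B comparison would have to carry a fitted relation across a gap of at least 19 years in which neither group has data. Group C could help only if its ages fell in the gap and if p16 changed with age in the same way in teratoma, malignant tumour and normal ovary. The plan gives no basis for either condition.

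**Step 5: is the A–B comparison planned?** Set side by side:

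- *Pointing to it:* the design is called case-control; Group B is called a control group and makes up 20 of the 62 specimens; section 2.1 states that "we hypothesized that abnormal P16 expression may be involved in its pathogenesis and germ stem cell proliferation", and abnormal expression needs a normal reference.
- *Pointing away:* the numbered aims concern tumours, for example "Compare the immunohistochemical expression of p16 between different histopathological types of OGCTs"; the scoring text in section 2.4 describes scores for tumours and lesions and does not describe scoring of normal ovary.

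The comparison is implied, not specified, so its consequence has to be stated conditionally.

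**The case against.** The strongest reply is that Group B may be only reference tissue. Section 2.4 mentions the normal ovaries in the same paragraph as the positive and negative staining controls, and no aim names them. On that reading, no A–B test would be run and the main tumour comparisons would be unaffected. This stands in part: comparisons within Group A do not depend on Group B, and the point must stay conditional. It does not rescue the design label. If Group B is not compared, calling the study a matched case-control study has even less support.

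It can also be said that matching may have been on something other than age. The documents do not exclude this, so a reader who infers that no matching of any kind took place goes further than the text. What the text shows is that A and B are not age-matched and that no other variable is named.

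A further reply is that the ages are openly reported, so a reader can see the imbalance. That is true, but the reader is also told that the groups are matched, and the two statements need reconciling.

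Finally, nothing says that Group B will enter the Aim 3 age correlation. The other parameters in that aim (type, grade, stage) apply to tumours, which suggests that it will not. The request on Aim 3 is therefore a clarification; no error has been shown there.

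**Conclusion.** The point holds. The word matched is unsupported as written, and for Groups A and B it cannot mean age: the ranges are 19 years apart, the medians differ by 33.5 years and the mean ages by 27.9 to 41.2 years. If p16 is compared between these groups, the difference cannot be separated from age, and the planned tests do not address this.

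A reader might infer that the A–B result will be biased, or by how much. The documents do not support that. They do not say whether p16 varies with age, so the bias could be nil, and its size and direction are unknown. What is established is that the two effects cannot be separated, which follows from the age ranges alone.

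Whether comparisons involving Group C share the problem cannot be judged, because its ages are missing. Calling that group equal is not explained and may refer only to its size. The conclusion rests on the stated ages being correct and on the available text; some pages were removed before review.

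**What to change.** 1. In section 2.4, delete the word matched, or state the variable actually used for matching and say that it was not age for A versus B.
2. State whether Group B is scored for p16. If it is, present A versus B as descriptive, give the complete age separation as a limitation, and do not attribute a difference to neoplasia.
3. Report the age range and median of Group C from the pathology reports. Rest benign-versus-malignant inference on A versus C only to the extent that those ages overlap.
4. In section 2.5, state that the Aim 3 correlation of p16 with age is run within the tumour groups and not pooled with Group B.

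The cost is some rewording of sections 2.4 and 2.5 and one line of data on Group C. No new specimens are needed. The real downside is that the study gives up an inferential claim against normal ovary, and A versus C may prove limited too once Group C's ages are known.
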